15. COSTS AND PAYMENTS

15.1. Research Study Costs:

Screening and clinical assessment of the patient prior to the procedure will be no different than what typically occurs prior to conventional radiation therapy. Therefore, a patient's insurance will be billed for all tests and imaging associated with this evaluation. The cost of the procedure itself will be billed to the patient's insurance company under an appropriate code. This will include all operative, facility-based and hospital-based charges. Follow-up assessment also is no different than what typically occurs following a conventional radiotherapy and treatment for this population

Page 31 of 52

of patients. Therefore, the patient's insurance will be billed for all tests and imaging associated with the follow-up visits.

15.2. Research Study Payments:

There will be no financial reimbursement to the patient for participation in this evaluation. Some data management, salary support and supplies will be provided by Accuray Inc., Sunnyvale, CA (project sponsor).

П

Appendix II: Performance Status Scales		

ECOG PERFORMANCE SCALE

- 0 Fully active, able to carry on all predisease activities without restriction (Karnofsky 90-100).
- 1 Restricted in physically strenuous activity but ambulatory and able to carry out work of a light or sedentary nature. For example, light housework, office work (Karnofsky 70-80).
- 2 Ambulatory and capable of all self-care but unable to carry out any work activities. Up and about more than 50% of waking hours (Karnofsky 50-60).
- 3 Capable of only limited self-care, confined to bed or chair 50% or more of waking hours (Karnofsky 30-40).
- 4 Completely disabled. Cannot carry on any self-care. Totally confined to bed or chair (Karnofsky 10-20).

Appendix III: AJCC STAGING SYSTEM, 6TH EDITION, PROSTATE

Primary Tumor, Clinical (T)

TX Primary tumor cannot be assessed

T0 No evidence of primary tumor

T1 Clinically inapparent tumor not palpable or visible by imaging

T1a Tumor incidental histologic finding in 5% or less of tissue resected

T1b Tumor incidental histologic finding in more than 5% of tissue resected

T1c Tumor identified by needle biopsy (e.g., because of elevated PSA)

T2 Tumor confined with prostate*

T2a Tumor involves less than 1/2 of one lobe

T2b Tumors involves greater than ½ of one lobe but < 2 lobes

T2c Tumor involves both lobes

T3 Tumor extends through prostate capsule**

T3a Extracapsular extension (unilateral or bilateral)

(סובעדונים: ברונעדונים בדרונים ברונעדונים ברונעדונים ברועדונים (סובעדונים ומנדים ברונעדונים ברונעדים ברונעדונים ברונעדים ב

*Note: Tumor found in one or both lobes by needle biopsy, but not palpable or reliably visible by imaging, is classified as T1c

**Note: Invasion into the prostatic apex or into (but not beyond) the prostatic capsule is not classified as T3, but as T2.

Regional Lymph Nodes (N)

Clinical NX Regional lymph nodes cannot be assessed

N0 No regional lymph node metastasis

N1 Metastasis in regional lymph node or nodes

Pathologic pNX Regional nodes not sampled

pN0 No positive regional nodes pN1 Metastases in regional node(s)

Distant Metastasis (M)*

MX Presence of distant metastasis cannot be assessed (not evaluated by any modality)

M0 No distant metastasis

M1 Distant metastasis

M1a Nonregional lymph node(s)

M1b Bone(s)

M1c Other site(s) with or without bone disease

*Note: When more than one site of metastasis is present, the most advanced category is used; pM1c is most advanced.

Appendix IV: Data Collection Documents

Refer to: http://eventa.kikamedical.com/accuray-prostate/

Appendix V: NCI Common toxicity criteria/RTOG/EORTC:

Refer to: http://ctep.cancer.gov/forms/CTCAEv3.pdf

Appendix VI: AUA, SF-12, EPIC, SHIM, USMD Questionnaires:

American Urological Association (AUA) symptom index: was developed to help men determine how bothersome their urinary symptoms are and to check the effectiveness of treatment.⁶ This questionnaire has also been adopted worldwide and is known as the International Prostate Symptom Score (IPSS). It is sometimes seen with a Quality of Life Scale at the end of the questionnaire.

Name:	Today's date:

(Circle one number on each line)	Almost never	Less than 1 time in 5	Less than half the time	About half the time	More than half the time	Almost always
Over the past month or so, how often have you had a sensation of not emptying your bladder completely after you finished urinating?	0	1	2	3	4	5
Over the past month or so, how often have you had to urinate again less than two hours after you finished urinating?	0	1	2	3	4	5
Over the past month or so, how often have you found you stopped and started again several times when you urinated?	0	1	2	3	4	5
Over the past month or so, how often have you found it difficult to postpone urination?	0	1	2	3	4	5
Over the past month or so, how often have you had a weak urinary stream?	0	1	2	3	4	5
Over the past month or so, how often have you had to push or strain to begin urination?	0	1	2	3	4	5
	None	1 time	2 times	3 times	4 times	5 or more times
Over the past month, how many times did you most typically get up to urinate from the time you went to bed at night until the time you got up in the morning?	0	1	2	3	4	5

 Quality of Life: If you were to spend the rest of your life with your urinary condition just the way it is now, how would you feel about that? Delighted, Pleased, Mostly satisfied, Mixed, Mostly dissatisfied, Unhappy, Terrible

SF-12 (Short Form)

 In general, would you say your health is excellent, very good, good, fair, or poor? Excellent ... Very Good ... Good ... Fair ... Poor ...

The following items are about activities you might do during a typical day. Does your health now limit you in these activities? If so, how much?

- 2) First, moderate activities such as moving a table, pushing a vacuum cleaner, bowling or playing golf. Does your health now limit you a lot, limit you a little, or not limit you at all. Limited a lot ... Limited a little ... Not limited at all ...
- 3. Climbing several flights of stairs. Does your health now limit you a lot, limit you a little, or not limit you at all? Limited a lot ... Limited a little ... Not limited at all ...
- 4. During the past four weeks, have you accomplished less than you would like as a result of your physical health? No ... Yes ...
- 5. During the past four weeks, were you limited in the kind of work or other regular activities you do as a result of your physical health? No ... Yes ...
- 6. During the past four weeks, have you accomplished less than you would like to as a result of any emotional problems, such as feeling depressed or anxious? No ... Yes ...
- 7. During the past four weeks, did you not do work or other regular activities as carefully as usual as a result of any emotional problems such as feeling depressed or anxious? No ... Yes ...
- 8. During the past four weeks, how much did pain interfere with your normal work, including both work outside the home and housework? Did it interfere not at all, slightly, moderately, quite a bit, or extremely? Not at all ... Slightly ... Moderately ... Quite a bit ... Extremely ...

These questions are about how you feel and how things have been with you during the past 4 weeks. For each question, please give the one answer that comes closest to the way you have been feeling.

- 9. How much time during the past 4 weeks have you felt calm and peaceful? All of the time ... Most of the time ... A good bit of the time ... Some of the time ... A little of the time ... None of the time ...
- 10. How much of the time during the past 4 weeks did you have a lot of energy? All of the time ... Most of the time ... A good bit of the time ... Some of the time ... A little of the time ... None of the time ...
- 11. How much time during the past 4 weeks have you felt down? All of the time ... Most of the time ... A good bit of the time ... None of the time ...
- 12 During the past 4 weeks, how much of the time has your physical health or emotional problems interfered with your social activities like visiting with friends, relatives etc? All of the time ... Most of the time ... Some of the time ... None of the time ...

П

EPIC-26

The Expanded Prostate Cancer Index Composite

Short Form

This questionnaire is designed to measure Quality of Life issues in patients with Prostate cancer. To help us get the most accurate measurement, it is important that you answer all questions honestly and completely.

Remember, as with all medical records, information contained within this survey will remain strictly confidential.

Today's Date (please enter date when survey comp	eted): Monthl	DayYear	_
Name (optional):		_	
Date of Birth (optional): MonthDay	Year		

	Do Not Mark in This Space
	23/
,	
ne number)	26/
0	4000
e number)	27/
weeks?	
e Big n Problem 4 4	28/ 29/ 30/
4	31/
4	33/
weeks?	34/
	34/

							Mark : This Space
1. Ove	r the past 4 weeks, how often ha	ave you le	eaked urine?				
11 000000	More than once a day						
	About once a day						
	More than once a week			e one numb	er)		23/
	About once a week		4				17.69
	Rarely or never		5				
2. Whic	h of the following best describes	your urin	ary control du	iring the las	t 4 weeks?		
	No urinary control whatsoev	er		1			
	Frequent dribbling			2	(Circle one n	umber)	26/
	Occasional dribbling		***********	3			
	Total control			4			
	many pads or adult diapers per oing the last 4 weeks?	day did yo	ou usually use	e to control le	eakage		
	None			0			
	1 pad per day			1			
	2 pads per day			2	(Circle one n	umber)	27/
	3 or more pads per day			3			
4. How	big a problem, if any, has each o	f the follo	wing been fo	r you during	the last 4 wee	eks?	
	Circle one number on each line)						
a.	Dripping or leaking urine	No Problem 0	Very Small Problem 1	Small Problem 2	Moderate Problem 3	Big Problem 4	28/
b.	Pain or burning on urination	0	1	2	3	4	29/
c.	Bleeding with urination	0	1	2	3	4	30/
d.	Weak urine stream						
	or incomplete emptying	0	1	2	3	4	31/
e.	Need to urinate frequently durin	ıg					
	the day	0	1	2	3	4	33/
5. Over	all, how big a problem has your u			r you during	the last 4 we	eks?	
	No problem						
	Very small problem						
	Small problem			(Circle one	number)		34/
	Moderate problem						
	Big problem,		5				
DEC-SE 6 200	2 Commisht	2002 The	University of M	ichigan All vie	hts reserved		

пппппппп52

a. Urgency to have	No Problem	Very Small Problem	Small Problem	Moderate Problem		
a bowel movement	. 0	1	2	3	4	49
			2	3	4	49
Increased frequency of bowel movements	. 0	1	2	3	4	50
		17.1		>251	600	1.75
Losing control of your stools		1	2	3	4	52
Bloody stools e. Abdominal/ Pelvic/Rectal pain		1	2	3	4	53 54
7. Overall, how big a problem have your			_			
No problem			ou during	tile last 4 we	eksr	
Very small problem						
Small problem			(Cirolo on	number)		55
Moderate problem			(Circle one	number)		55
Big problem						
How would you rate each of the follow						
			Poor to None	Poor Fair	Good Very	
a. Your ability to have an erection	on?		1	2 3	4 5	57
b. Your ability to reach orgasm ((climax)?		1	2 3	4 5	58
9. How would you describe the usual QU	JALITY of	your erections	s during th	e last 4 week	s?	
None at all				1		
Not firm enough for any sexual a	ctivity		****	2		
Firm enough for masturbation an	d foreplay	only		3 (Circle	e one number)	59
Firm enough for intercourse				4		
10. How would you describe the FREQU	ENCY of y	our erections	during the	e last 4 week	s?	
I NEVER had an erection when I						
I had an erection LESS THAN HA	ALF the tin	ne I wanted or	ne	2		
I had an erection ABOUT HALF t	he time I v	vanted one		3 (Circle	e one number)	60
I had an erection MORE THAN H	ALF the ti	me I wanted o	ne	4		
I had an erection WHENEVER I	wanted on	e		5		

						Do Not Mark in This Space
11. Overall, how would you rate your ability	to funct	ion sexually	during the la	ast 4 weeks?		
Very poor		1				
Poor		2				
Fair		3	(Circ	le one numbe	r)	64/
Good	Good					
Very good		5				
during the last 4 weeks? No problem	**********	2 3 4 5		de one numbe	i.	68/
(Circle one number on each line)	No roblem	Very Small Problem	Small Problem	Moderate Problem	Big Problem	
a. Hot flashes	0	1	2	3	4	74/
b. Breast tenderness/enlargement	0	1	2	3	4	75/
- FE dd	0	1	2	3	4	77/
 Feeling depressed 						
d. Lack of energy	0	1	2	3	4	78/

THANK YOU VERY MUCH!!

EPIC-SF 6.2002

Copyright 2002. The University of Michigan. All rights reserved.

Г

SEXUAL HEALTH INVENTORY FOR MEN (SHIM)

PATIENT NAME:	TODAY'S DATE:
---------------	---------------

PATIENT INSTRUCTIONS

Sexual health is an important part of an individual's overall physical and emotional well-being. Erectile dysfunction, also known as impotence, is one type of very common medical condition affecting sexual health. Fortunately, there are many different treatment options for erectile dysfunction. This questionnaire is designed to help you and your doctor identify if you may be experiencing erectile dysfunction. If you are, you may choose to discuss treatment options with your doctor.

Each question has several possible responses. Circle the number of the response that **best describes** your own situation. Please be sure that you select one and only one response for **each question**.

OVER THE PAST 6 MONTHS:

How do you rate your confidence		Very Low	Low	MODERATE	Нідн	VERY HIGH
that you could get and keep an erection?		1	2	3	4	5
2. When you had erections with sexual stimulation, how often were	No Sexual ACTIVITY	ALMOST NEVER OR NEVER	A Few Times (MUCH LESS THAN HALF THE TIME)	SOMETIMES (ABOUT HALF THE TIME)	MOST TIMES (MUCH MORE THAN, HALF THE TIME)	ALMOST ALWAYS OR ALWAYS
your erections hard enough for penetration (entering your partner)?	0	1	2	3	4	5
3. During sexual intercourse, how often were you able to maintain your	DID NOT ATTEMPT INTERCOURSE	ALMOST NEVER OR NEVER	A FEW TIMES (MUCH LESS THAN HALF THE TIME)	SOMETIMES (ABOUT HALF THE TIME)	MOST TIMES (MUCH MORE THAN, HALF THE TIME)	ALMOST ALWAYS OR ALWAYS
erection after you had penetrated (entered) your partner?	0	1	2	3	4	5
4. During sexual intercourse, how difficult was it to maintain your	DID NOT ATTEMPT INTERCOURSE	EXTREMELY DIFFICULT	VERY DIFFICULT	DIFFICULT	SLIGHTLY DIFFICULT	Not Difficult
erection to completion of intercourse?	0	1	2	3	4	5
5. When you attempted sexual intercourse, how often was it	DID NOT ATTEMPT INTERCOURSE	ALMOST NEVER OR NEVER	A Few Times (MUCH LESS THAN HALF THE TIME)	SOMETIMES (ABOUT HALF THE TIME)	MOST TIMES (MUCH MORE THAN, HALF THE TIME)	ALMOST ALWAYS OR ALWAYS
satisfactory for you?	0	1	2	3	4	5

Add the numbers corresponding to questions 1-5.	TOTAL:	
---	--------	--

The Sexual Health Inventory for Men further classifies ED severity with the following breakpoints: 1-7 Severe ED 8-11 Moderate ED 12-16 Mild to Moderate ED 17-21 Mild ED

UTILIZATION OF SEXUAL MEDICATIONS/DEVICES

This questionnaire is designed to assess the use of erectile aids among patients treated for prostate cancer. To help us get the most accurate measurement, please answer all questions honestly and completely. You may refuse to answer any questions for any reason. All information contained within this survey will remain strictly confidential. Thank you for participating and for helping us improve the quality of care for prostate cancer patients.

cancer patients.			
TODAY'S DATE (please enter data when survey completed) Month	Day	Year	

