2. OBJECTIVES

PRIMARY OBJECTIVES: The primary study goal is to document the efficacy of the CyberKnife procedure, where efficacy is defined by biochemical Disease-Free Survival (bDFS), using Phoenix and ASTRO definitions, at 5 years. This will be accomplished through testing the primary efficacy hypotheses detailed in Sections 1.1.5 and 11.2. Additionally, descriptive statistics will be provided comparing the CyberKnife SRS bDFS rate to published HDR monotherapy bDFS rates reported in the literature. A second primary study goal is to accurately measure the rates of acute and late grade 3-5 gastrointestinal and genitourinary toxicity observed during the five years following CyberKnife SRS for prostate cancer.

SECONDARY OBJECTIVES: to measure the following in the study population: Rates of local failure, distant failure, clinical disease-free survival, disease-specific survival, and overall survival; quality of life (QOL) in generic and organ-specific domains; work effort required in treatment planning and delivery of CyberKnife SRS.

Patients will be followed annually to 10 years, to collect additional data for descriptive analysis.

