11.4.2. SECONDARY OBJECTIVES

1. Local and Distant Tumor Control

As defined in Section 9.4, the failure to achieve local and distant tumor control will be documented for each patient. These rates will be summarized and descriptive statistics (standard deviations, confidence intervals) will calculated.

2. Quality of Life Assessments

The SF-12 total score, AUA score, EPIC-26 total score and the EPIC-sexual domain sub score are used to quantify quality of life (QoL) at baseline and repeatedly during the post treatment period (see Section 9.0). We will use the generalized estimating equation (GEE) method to provide valid inferences. This method was originated to make inference about average behavior, where the dependent variable depends not only on the "explanatory" variable (time measured in months) but also on the correlation of a patient's repeated measurements. The GEE approach fits the model to the observed data as closely as possible, weighting each patients' "cluster" of measurements over time inversely to its variance - covariance matrix. With this method, no imputations are required and all data recorded is use in the analysis. Other important features of GEE are that no distributional assumptions for the dependent variable are required to use the method and in most cases valid inferences are provided even when the correlation structure is miss-specified. For each score, we will use GEE to fit a straight line to patients' longitudinal course of repeated values. We hypothesize that immediately following treatment, the GU & GI subsections of the EPIC-26 and the AUA will demonstrate a worsening of GU and GI function, but this will return to normal with time. We further hypothesize that the sexual function subset of the EPIC-26 will show gradual worsening function relative to baseline over the five-year follow-up period. These QOL outcomes will be compared to those reported in other prospective studies using the same instruments, including RTOG 0232

and 0415. We hypothesize that the slope of a fitted line will not be significantly less than zero; that is, QoL will be maintained throughout the assessment period.

3. Adverse Events

All adverse events will be recorded on the case report forms. For both acute (<=90 days of treatment start) and late (>90 days of treatment start), the frequency and proportion of each type of adverse event will be presented in tabular form, on both a per-patient and a per-event basis.

4. Survival

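### The SF-12 is analysed only as one undefined total, so a physical decline could be offset by an emotional gain and read as maintained quality of life

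*Combined protocol and SAP*

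**What the plan says.** Section 11.4.2, item 2, lists the quality-of-life outcomes: "The SF-12 total score, AUA score, EPIC-26 total score and the EPIC-sexual domain sub score are used to quantify quality of life". The total is the only SF-12 quantity named. The model is the same for every outcome: "For each score, we will use GEE to fit a straight line to patients' longitudinal course of repeated values". The reading of the result is also common to all: "We hypothesize that the slope of a fitted line will not be significantly less than zero; that is, QoL will be maintained throughout the assessment".

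Section 9.3.1 describes the SF-12 as a generic health-status measure obtained by scoring standard questions. Neither it nor Appendix VI says how the twelve answers are coded, weighted or reversed, or whether a high total is good.

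The form in Appendix VI separates causes in its own wording. Items 4 and 5 ask about limits from physical health (item 4: "During the past four weeks, have you accomplished less than you would like as a result of your physical health"). Items 6 and 7 ask about limits from emotional problems (item 6: "have you accomplished less than you would like to as a result of any emotional problems, such as feeling depressed or anxious"). Item 12 joins the two: "how much of the time has your physical health or emotional problems interfered with your social activities".

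**The concern.** A single total can stay flat while its parts move in opposite directions. After treatment of a cancer it is conceivable that mood recovers while physical function falls through treatment effects or five years of ageing. One straight line through the total would then show little slope.

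The decision rule makes this matter more. It takes lack of significance as maintenance, with no margin, so anything that weakens the test pushes towards the favourable conclusion.

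The missing scoring rule is a separate gap that does not depend on any offset. The printed answers run in opposite directions: being calm or energetic all of the time is good (items 9 and 10), while feeling down or being hindered socially all of the time is bad (items 11 and 12). Until coding and direction are fixed, two analysts could form different totals, and a slope below zero has no settled meaning.

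**Working it through.** **Plan figures.** The documents give no power, SD, margin or sample size for the SF-12, so there is no SF-12 figure to reproduce. The only number borrowed is the evaluable sample size in Section 11.3, which checks: [0.84·√(0.945·0.055) + 1.645·√(0.90·0.10)]² / 0.045² = 231.7, so 232; and 232/0.92 = 252.2, so 253.

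**Items as printed, each coded 0 to (levels − 1).**

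| Group | Items | Span |
|---|---|---|
| Physical | 2, 3, 4, 5, 8 | 2+2+1+1+4 = 10 |
| Emotional | 6, 7, 9, 11 | 1+1+5+3 = 10 |
| General or mixed | 1, 10, 12 | 4+5+3 = 12 |

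In a simple sum the clearly physical and clearly emotional items have equal spans, so full offset is arithmetically possible.

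**Illustration with the planned type of test (a slope).** From the documents: n = 232, and SF-12 visits at months 0, 1, 6, 12, 24, 36, 48 and 60 (Section 9). Assumed: complete data, SD 8 to 12 on each part's scale, within-patient correlation ρ of 0.4 to 0.6 (exchangeable), correlation r of 0 to 0.5 between the two parts, a total equal to the mean of the two parts, and a one-sided 5% test (Section 11.4.2 states neither level nor sidedness).

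- Sum of squares of visit times: 7957 − 187²/8 = 3585.9.
- SE of a part's slope = SD·√(1−ρ) / √(232·3585.9). With SD 10 and ρ 0.4: 7.746/912.1 = 0.00849 per month.
- SE of the total's slope = that value × √((1+r)/2).
- Power = Φ(|slope|/SE − 1.645).

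Example, SD 10, ρ 0.4, physical decline of 2 points over 60 months. Physical score: (2/60)/0.00849 = 3.92, and Φ(2.28) = 0.99. Total when the emotional part rises by 1 point and r = 0: slope (2−1)/2/60 = 0.00833, SE 0.00849·√0.5 = 0.00601, ratio 1.39, and Φ(−0.26) = 0.40.

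Ranges over all the assumed values:

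| Physical decline | Physical score | Total, no emotional change | Total, half offset | Total, full offset |
|---|---|---|---|---|
| 2 points | 0.95 to >0.99 | 0.60 to >0.99 | 0.24 to 0.68 | 0.05 |
| 3 points | >0.99 | 0.88 to >0.99 | 0.41 to 0.94 | 0.05 |
| 5 points | >0.99 | >0.99 | 0.76 to >0.99 | 0.05 |

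For the 2-point decline with half offset, the plan's rule would report maintenance in 1 − 0.68 = 32% to 1 − 0.24 = 76% of trials. With full offset it would do so in 95%.

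**Cross-check, simple change from baseline.** SD of change 10, n = 232, r = 0 to 0.3, SD of the total = 10·√((1+r)/2), power = Φ(δ/(SD/√232) − 1.645).

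- 3-point physical decline: 99.8% on its own score; on the total, 88–94% with no emotional change, 24–29% with a 2-point gain, 5% with a 3-point gain.
- 2-point physical decline: 92% on its own score; on the total, 60–70% with no emotional change, 5% with a 2-point gain.
- Both parts falling by 2 points: on the total, δ = 2 and the SE is 7.07/√232 = 0.464 (r = 0) or 8.06/√232 = 0.529 (r = 0.3), giving 99.6% and 98.4%, against 92% on the physical score alone.

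**The case against.** The strongest reply is that this is a secondary, uncontrolled result that drives no trial decision, and that physical effects are also captured elsewhere. That largely stands. ECOG performance status, which grades activity, is recorded through year 5. The AUA score and the EPIC sexual sub score are modelled, hypotheses are stated for the EPIC GU, GI and sexual subsections, SHIM is collected, and grade 3 or higher GI and GU toxicity is a primary objective. A reader might infer that the SF-12 alone could reveal a physical decline; the documents do not support that. However, ECOG is coarse and has no stated analysis, and the other instruments are mainly organ-specific and do not ask about moderate activity or climbing stairs.

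A reader might also infer that Section 2 is contradicted, because it speaks of "quality of life (QOL) in generic and organ-specific domains". The natural reading is that generic health is one domain and the organ-specific ones are the others. A generic total can meet that objective, and no SF-12 components are promised.

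Third, the low power figures need an emotional gain that nothing in the documents predicts, and a total gains sensitivity when both parts fall. Both points stand. So does the observation that a patient form need not print a scoring key; the gap is that no section supplies one. Finally, item responses are kept, so component scores could be derived later. Choosing them after seeing the data would, however, lose the benefit of pre-specification.

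**Conclusion.** The point holds in limited form. Section 11.4.2 commits the SF-12 to a single total with no defined scoring or direction, and its reading rule leans towards a favourable conclusion. Masking of a physical decline is possible, not shown. Its size depends on SDs, correlations, trends and item weights that the documents do not give. Under the assumptions above the loss runs from slight (a 5-point decline with no offset) to complete (equal and opposite trends), and it reverses when both parts worsen. It would be wrong to conclude that the plan will hide a decline, or that the 5% figure is the expected power. Only the secondary quality-of-life statement is affected; the bDFS and toxicity tests are untouched.

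**What to change.** In Section 11.4.2, item 2, replace the SF-12 total with a physical and a mental summary score from the same twelve items. Name one published scoring rule in advance; it must also fix the direction of each score and the handling of items 1, 10 and 12. Model each score with the GEE method already planned, and report the estimated change with its confidence interval. Keep any total as descriptive.

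Splitting the score does not cure the reading rule, so also delete the inference that a non-significant slope means quality of life was maintained.

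Cost: a short edit to the analysis text, one extra model and one extra secondary test. No new data are needed.
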